Response to Diaphragmatic Pacing in Subjects with Pompe Disease

NCT02354651

Document Date: 02/15/2017

STATISTICAL ANALYSIS PLAN

Testing:

Pulmonary Function: Spirometry, maximal respiratory pressures, and occlusion pressure ($P_{0.1}$, a Clinical estimate of drive) will be completed per American Thoracic Society guidelines. Pacing will be turned off during these tests. In addition, the breathing pattern (breath flows, volumes, timing, end-tidal CO_2) will be calculated continuously while testing on MV support, during pacing, and for 1 hour after pacing. These measures will be obtained when patients are able to come to the testing site, or when the study team is able to travel to the patient's local area.

Ventilator Weaning: To evaluate weaning effects of diaphragm pacing, the duration of ventilator-free breathing (timing, volume, minute ventilation) will be recorded remotely. We will query each subject's ventilator data chip when possible to track weaning.

Electrophysiology: We will compute root mean square (RMS) of the spontaneous (unpaced) diaphragm EMG during resting MV, unassisted breathing and MIP tests. The implanted intramuscular electrodes permit us to conduct quantitative, longitudinal electrophysiological tests of phrenic motor function previously only feasible in animals; these *exploratory tests* include power spectral analysis and spike sorting to identify active motor units.

Data Interpretation: Outcomes for both aims are largely quantitative and continuous. Sample distributions and summary statistics will be calculated for each outcome and represented with box plots. Data transformation of non-linear distributions will be done if needed. Within-session measurements, when possible, will be evaluated using repeated measures ANOVA, with volume, rate, and ventilation as primary outcomes. Between-session outcomes of interest include off ventilator function (**primary outcome measure**) and breathing pattern/ventilation. These will be quantified with repeated measures ANOVA.

Expected Outcomes: Completion of this project will generate needed information concerning the rate, extent and duration of functional gains with diaphragm pacing. Within-session measurements will elucidate baseline diaphragm/phrenic function in MV-dependent adults with Pompe, and provide needed insights concerning neuromuscular modulation by diaphragm pacing. Between-session measurements will yield important data concerning the efficacy of diaphragm pacing to restore phrenic function and to reduce MV dependence over time.

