The study group will consist of twelve male or female subjects 2-65 years of age with a diagnosis of Pompe disease as defined by mutational analysis, GAA enzyme activity assay in blood spot and/or fibroblast culture less than 40% of control values, as well as clinical symptoms. In addition, subjects will be eligible if they have met the clinical eligibility for NeuRx DPS implantation. All subjects will have a history of mechanical ventilation (MV) dependence, defined as a requirement of six or more hours invasive or non-invasive MV support daily for at least 21 days in duration [10]. Subjects currently on GAA replacement therapy will continue protein replacement during the study.

Subjects will be recruited either via self-referral to the research team (e.g. after discovering the study on ClinicalTrials.gov), or referral from the surgeon who conducts the implantation surgery. The surgeon will provide subjects with the contact information of the study team, so that they may inquire to us about the study.

Exclusionary Criteria:

The subject must not:

- Be participating in another treatment study using a device for diaphragm pacing
- Be unable to complete pulmonary function testing
- Be pregnant, or become pregnant throughout participation in the study. If a subject may be pregnant, a pregnancy test will be performed, or results of a recent test will be used to confirm.

Study design:

Subjects with Pompe disease who are having NeuRx DPS implantation will be invited to participate in this study. This procedure is part of the subject's clinical care, and is not done for this or any other research project. Baseline data will be entered into the study record from clinical testing completed within 12 months of NeuRx DPS implant. After placement of DPS, study assessments will be completed at Days 3, 14, 90 and 180 per table of events on page 8.

Testing:

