routinely uses MV throughout the day, the sensing equipment can be placed in series to the breathing tubes. Resting breathing will be recorded under the following conditions: (1) using the subject's routine daytime ventilatory support (ventilator, BiPAP, ETC); (2) using the subject's routine daytime ventilatory support plus the diaphragm pacer; (3) using no support or the lowest support needed to maintain baseline minute ventilation (if the subject uses reduced or no settings routinely); (4) using no support or the lowest support needed to maintain baseline minute ventilation plus the diaphragm pacer (if the subject uses reduced or no settings routinely). Subjects will rest for a minimum of 30 minutes between each condition, and tests may be scheduled over two consecutive days as needed. Resting Breathing Pattern will be completed at Screening, Baseline, Day 5, Day 14, Day 30, Day 90, and Day 180. During this testing, subjects will not be taken below their lowest tolerated ventilator settings.

Respiratory Muscle Endurance Test: This test will begin after subjects rest for a minimum of one hour. Subjects will be tested in the seated position while breathing through a mouthpiece with nose clip. When a steady state breathing pattern has been reached (noted by stable tidal volumes for at least 30 seconds), subjects will be instructed how to maintain the breathing rate and volume, with the use of visual feedback on a computer. A threshold inspiratory load equivalent to 35% of the maximal inspiratory pressure will be placed on the inspiratory port of the mouthpiece. Subjects will be instructed to maintain the established breathing pattern during loaded breathing. The test will end when the subject cannot open the threshold valve for 3 consecutive breaths, or when the subject can no longer subjectively tolerate the test and must remove the mouthpiece. Loaded breathing typically lasts between 2-10 minutes. Respiratory Muscle Endurance Testing will be completed at Screening, Baseline, Day 90, and Day 180.

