We will evaluate changes in average respiratory rate and volume, integrated EMG, and daily independent breathing time, between 0 and 6 months. Since this is an observational pilot study, data will be largely descriptive. However, the data are largely quantitative and continuous. Sample distributions and summary statistics will be calculated for each of these outcomes. Data transformations will be done if non-linear distributions exist, and repeated measures ANOVA (or non-parametric) will quantify recovery at 6 months.

7. Possible Discomforts and Risks:

Pulmonary Function Testing

Pulmonary function testing is used routinely in clinical medicine and has no inherent complications. Pulmonary function testing will be completed by the study team on Day 5, 14 and 180 after NeuRx DPS implantation. If possible, the study team will complete pulmonary function testing the day prior to NeuRx DPS implantation.

Although sustained (several minutes to several hours), intensive inspiratory loading can produce elevations in oxygen consumption, mean arterial pressure and diminish cardiac output, brief

periods of loading (<30 seconds) have not been shown to cause significant changes in cardiac parameters (Coast et al., 1988). Nevertheless, we have designed the protocol to include strict limits on baseline and exertional vital signs, in order to minimize the imposed cardiorespiratory work. Due to the brief duration of testing and training procedures, the incidence of blood gas dysfunction is extremely low. Nevertheless, end-tidal CO₂ and oxygen saturation will be monitored continually.

Respiratory testing may elicit transient fatigue or shortness of breath that resolves within several seconds of completion. Frequent rests are included to prevent or minimize these systems.

Phrenic Nerve Function Evaluation with EMG

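### Between-session breathing pattern is tested by repeated measures ANOVA on travel-dependent sessions, and neither document says which visits enter or how incomplete subjects are handled

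*SAP*

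**What the plan says.** Under Testing (Pulmonary Function), the SAP says that spirometry, respiratory pressures and breathing-pattern measures are obtained "when patients are able to come to the testing site, or when the study team is able to travel to the patient's local area". Under Data Interpretation it lists two between-session outcomes: off-ventilator function, which is primary, and breathing pattern/ventilation. It then says: "These will be quantified with repeated measures ANOVA". The same paragraph provides for description: "Sample distributions and summary statistics will be calculated for each outcome and represented with box plots". Expected Outcomes promises "information concerning the rate, extent and duration of functional gains with diaphragm pacing".

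The protocol's Data analysis section looks at change from 0 to 6 months, calls the study an observational pilot with largely descriptive data, and says that "repeated measures ANOVA (or non-parametric) will quantify recovery at 6 months".

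The protocol gives three lists of post-implant days that bear on this outcome:
- Resting Breathing Pattern, which agrees with the Schedule of Assessments: "Resting Breathing Pattern will be completed at Screening, Baseline, Day 5, Day 14, Day 30, Day 90, and Day 180".
- Study design: "study assessments will be completed at Days 3, 14, 90 and 180 per table of events on page 8".
- Section 7, Pulmonary Function Testing: "Pulmonary function testing will be completed by the study team on Day 5, 14 and 180 after NeuRx DPS implantation". The Testing section counts resting breathing pattern among the pulmonary function tests.

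In the text available for review, neither document says which sessions enter the between-session ANOVA or how a subject with a missing session is treated.

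**The concern.** The plan makes attendance conditional and then names a method that, in its classical form, needs every included visit from every subject. With 12 subjects, each exclusion is costly.

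The documents leave open which of two analyses is meant. One uses all visits, which the rate and duration of gains would need. The other compares baseline with Day 180, which is how the protocol's 0-to-6-month wording can be read. The first risks losing many subjects. The second loses few, but gives no estimate of the course over time.

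Under either reading, the estimated 6-month change is biased if attendance depends on how well the subject is responding. That is plausible in ventilator-dependent patients who must travel or be visited. The documents do not indicate the direction.

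**Working it through.** **Inputs from the documents.** There are twelve subjects. The post-implant visits number five (Days 5, 14, 30, 90, 180), four (Days 3, 14, 90, 180) or three (Days 5, 14, 180), depending on the section. Baseline may come from clinical tests within 12 months of implant, and a study-team test the day before implant is made only if possible. The documents give no miss rate, SD, effect size or sample-size calculation, so there is no plan figure to reproduce.

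**Step 1: subjects left.** Assume each visit is missed independently with probability m = 10% or 20%. Expected complete subjects = 12 × (1 − m)^k, where k is the number of visits that can be missed.

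| Visits required | k | m = 10% | m = 20% |
|---|---|---|---|
| Five post-implant, baseline complete | 5 | 12 × 0.9^5 = 7.1 | 12 × 0.8^5 = 3.9 |
| Four post-implant, baseline complete | 4 | 7.9 | 4.9 |
| Three post-implant, baseline complete | 3 | 8.7 | 6.1 |
| Five post-implant, baseline also missable | 6 | 6.4 | 3.1 |
| Baseline and Day 180, baseline complete | 1 | 12 × 0.9 = 10.8 | 12 × 0.8 = 9.6 |
| Baseline and Day 180, both missable | 2 | 9.7 | 7.7 |

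Misses caused by illness or distance would tend to cluster within subjects. With beta-binomial misses (intra-subject correlation 0.1 to 0.5), 12 × B(a, b+5)/B(a, b) gives 7.8 to 9.5 subjects at 10% and 4.8 to 7.4 at 20% for five visits.

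**Step 2: precision of the 6-month change.** Simulation assumptions: n = 12, baseline present, five visits, unit outcome variance split into 0.8 exponentially decaying (range 180 days) and 0.2 visit noise, and a linear true gain reaching 0.5 SD at Day 180. The SD of the estimate at 10% / 20% independent misses is:
- subjects with all visits: 0.47 / 0.63 (clustered misses: 0.39 to 0.44 / 0.45 to 0.57);
- baseline/Day 180 pairs: 0.37 / 0.39;
- mixed model on all sessions: 0.37 / 0.38.

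The all-visits analysis therefore has an SD 0.47/0.37 = 1.27 and 0.63/0.38 = 1.66 times that of the mixed model. Pairs lose almost nothing. At 20%, 6% of replicates had fewer than two complete subjects and were excluded, so 0.63 applies only to the remainder.

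**Step 3: bias when attendance follows response.** The true gain is 0.50 and the base miss rate 20%, with a slope of 1 on the logit scale in either direction. Each cell shows the mean estimate when poor responders miss more / when good responders miss more.

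| Misses depend on | All-visit completers | Pairs | Mixed model |
|---|---|---|---|
| Last observed change | 0.77 / 0.18 | 0.62 / 0.36 | 0.51 / 0.51 |
| Current, unobserved change | 0.93 / −0.12 | 0.72 / 0.12 | 0.64 / 0.28 |

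Completer and pairs figures use 40,000 replicates. Mixed-model figures use 800, so their Monte Carlo error is about 0.38/√800 = 0.013. The mixed model was fitted with the covariance form that generated the data, which favours it.

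**The case against.** **The protocol points to a two-point comparison.** This largely stands. The protocol's analysis section frames the outcome as change from 0 to 6 months, and on that reading a mixed model brings no real gain in precision. The promise of rate and duration sits in a general statement of expected outcomes, not in an analysis rule. Bias from response-related attendance remains, and so does the absence of any rule.

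**ANOVA is not the only analysis.** Correct. Summaries and box plots are planned for each outcome and are not limited to completers, and the protocol allows a non-parametric alternative. A reader might infer that completers are all that will be reported, or that the SAP prescribes deleting incomplete subjects. Neither is stated. ANOVA is the only inferential method the SAP names here, and standard rank tests for repeated measures also need complete blocks.

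**Interval widths.** A reader might compute 95% half-widths of about 1.0 / 1.6 SD for all-visit completers and set them against about 0.7 SD for a mixed model. That overstates the case. The wide figures are paired-t intervals on completers. The pooled-error ANOVA interval is about 0.7 / 1.0 SD, with only about 88% coverage. The mixed model's narrower interval also partly reflects its own coverage of 91% to 93%. The SD of the estimate is the fairer comparison.

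**Some breathing measures may be remote.** The SAP's Ventilator Weaning paragraph records timing, volume and minute ventilation of ventilator-free breathing remotely, so part of this outcome may escape the travel condition. The sessions on ventilator support, during pacing and in the hour after it remain under that condition.

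**Miss rates are assumed.** They are. Day 5 may well be missed less often than Day 180, and either team or patient may travel.

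**Conclusion.** The gap is real and of minor to moderate severity. The SAP pairs conditional attendance with an ANOVA and states neither the visits entering it nor the treatment of incomplete subjects. If all five post-implant visits are required, about 7.1 / 3.9 of 12 subjects remain at 10% / 20% independent misses and precision falls materially. If baseline and Day 180 alone are compared, 10.8 / 9.6 remain and precision hardly changes. A mixed model then offers less bias when misses follow observed response, and the course over time. It does not remove bias when misses depend on unobserved status.

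Two stronger inferences are not supported. The travel condition does not undermine the primary outcome, because ventilator-free breathing is recorded remotely. The study also does not fall short of a stated power, because none is stated and it is a largely descriptive pilot. Every miss rate, mechanism and correlation used here is an assumption.

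**What to change.** For between-session breathing pattern/ventilation, replace repeated measures ANOVA with a linear mixed model (REML) on all available sessions. Use visit as a factor, a simple covariance and small-sample degrees of freedom. Report the 0-to-6-month change with a 95% CI, and the number observed and reasons missing at each visit. Give the simple baseline-to-Day 180 paired change as a check. If the sponsor keeps the ANOVA, the SAP should at least name the visits that enter and state a rule for missed sessions.

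The cost is SAP wording and a little programming, with no new data. There are two downsides. With 12 subjects the covariance must stay simple. Interval coverage may also be slightly below nominal: with Satterthwaite degrees of freedom it was 91% to 93% in simulation on the five-visit days and about 95% on the four-visit days. Kenward-Roger was not tried.

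Separately, reconcile the post-implant days in the protocol's Study design, Resting Breathing Pattern, Schedule of Assessments and section 7, so that the set of visits is fixed before analysis.
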